#### IV. Methodology

Although a pilot study has been published regarding injection sites as few as one for 100 U of BTX, there has not been a randomized study comparing fewer injections sites to what is commonly practiced (ten injection sites).

Patients diagnosed with OAB and that have failed first and second line treatments will be presented with all third line therapies including BTX, SNS, and PTNS. Patients choosing BTX will be offered an opportunity to enroll in this study. If patients are already clinical responders and currently receiving BTX therapy, they are eligible for randomization if they choose to participate in the study. If they had prior BTX and were clinical non-responders they will not be eligible. Clinical non-responders are patients who previously reported no subjective improvement in their symptoms by 3 months after their injection. If a patient was an initial responder (with subjective improvement reported by the patient), and the effect has since worn off, the earliest they can receive re-injection will be 3 months after their initial injection. All repeat injections will be done at with a minimum of 3 months in between injections.

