Consent to send out pre-screening activities may be done by telephone script with all elements of information sheet included. Participant agreement is consent to send prescreening activities. Once the participant is present for enrollment visit, a formal consent will be performed for study participation. Informed consent will be obtained from all patients prior to conducting any study activities. Consented patients will complete the OAB-g SF, ICIQ-SF, 3-day voiding diary and enrollment guestionnaire (demographics, medical history, concomitant medications, etc.) prior to study enrollment. A urinalysis (UA) will be collected at this visit as well and a urine culture (UCx) will be performed, if necessary. If the patient meets the eligibility criteria, they will be randomized (1:1) into the 3-injection site group or the 10injection site group. We plan on performing a stratified randomization so the number of BTX naïve and previous BTX responder patients will be equivalent in both arms in order to minimize selection bias. Patients will be blinded to the number of injections they will receive. Adverse events and concomitant medications will be assessed at each follow-up visit. A diary will also be completed, collected and reviewed at each follow-up visit. GRA will also be gathered at each follow up visit. Visual Analog Scores will be gathered at the end of the injection visit to assess for patient satisfaction, pain, and tolerability.

Patients will be asked to remain off any oral anticholinergic or beta-3 agonist medications, PTNS therapy, or any neuromodulation throughout the entirety of the study.

Patients will follow up two weeks post-injection (±7days) for an office visit. OAB-q SF, GRA, ICIQ-SF, 3-day voiding diary, UA and post void residual (PVR) will be collected. If necessary, a UCx will be ordered for evaluation.

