#### VI. Eligibility Criteria

Inclusion criteria:

- Women and men  $\geq$  18 years of age
- Self-reported failed conservative care of behavioral modifications and/or oral medications for the treatment of OAB
- Average urinary frequency of ≥ 8 voids per day as recorded on initial 3-day voiding diary
- Self-reported bladder symptoms > 3 months
- Discontinued antimuscarinics/beta-3 agonists for 2 weeks prior to study enrollment.
   May restart antimuscarinics/beta-3 agonists if indicated 6 weeks after Botox injections.
- Previous onabotulinumA injection at least three months prior to study enrollment
- Capable of giving informed consent
- Capable and willing to follow all study-related procedures

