#### Data analyses

A biostatistician will perform all statistical analyses using SAS or similar statistical software. Descriptive statistics will be calculated. A completer analysis will be conducted for those who finish the study per protocol. The primary endpoint will be assessed comparing incontinence episodes per day at 3 months after BTX injection. This comparison will also be made for all other visits using t-tests or chi-square tests, as appropriate.

Secondary endpoints will include adverse events and comparisons between 3-site and 10-site groups looking at the GRA responses between 3-site and 10-site groups at 3 months (± 14 days) post injection, 3-day voiding diary and OABq-SF and ICIQ-SF at 3 months (± 14 days) post-injection. We will also compare post-injection VAS scores to assess for tolerability, satisfaction, and pain. Changes from baseline will also be analyzed. This comparison will also be made for all other visits using appropriate statistical tests.

In addition to a completer analysis, we also plan on conducting an intent to treat analyses which will identify any subject not assessed at 3 months after the first BTX injection as a treatment failure. In order to assess for all possible situations, 4 different scenarios will be run: 1) All dropouts will be considered non-responders for both groups 2) All dropouts will be considered responders for both groups, 3) Dropouts in the BTX 10 group will be considered responders and those in the BTX 3 group, non-responders, and 4) Dropouts in the BTX 10 group will be considered non-responders while those in the BTX 3 group, responders.

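### The inclusion list requires a previous onabotulinumtoxinA injection, which shuts out the BTX-naive patients whom the Methodology recruits and stratifies

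*Combined protocol and SAP*

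**What the plan says.** Section VI, inclusion criteria, lists as an item of its own: "Previous onabotulinumA injection at least three months prior to study enrollment". It carries no qualifier for patients who have never been treated.

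Section IV (Methodology) describes the population differently. Patients for whom first- and second-line treatment has failed are shown all third-line options, and "Patients choosing BTX will be offered an opportunity to enroll in this study". Earlier BTX comes in only as a condition. For responders: "If patients are already clinical responders and currently receiving BTX therapy, they are eligible for randomization if they choose to participate in the study". For non-responders: "If they had prior BTX and were clinical non-responders they will not be eligible". The three-month interval appears there as the minimum wait before a responder whose benefit has worn off is injected again.

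On allocation, the same section says: "We plan on performing a stratified randomization so the number of BTX naïve and previous BTX responder patients will be equivalent in both arms".

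The exclusion criteria in section VI remove previous non-responders to BTX. They do not mention patients without earlier BTX.

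**The concern.** Every inclusion criterion has to be met, so an item that presupposes an earlier injection fails every patient who has had none. The Methodology needs those patients, because they make up one of its two randomization strata. Both statements cannot hold.

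The eligibility list is the operative text for screening. Followed literally, it limits the trial to people already known to respond to BTX. The primary aim in section III is not limited in that way, and a non-inferiority result from previous responders alone would not cover first-time patients. If staff follow the Methodology instead, each naive patient enters against a written criterion. Section VIII (Data Safety Monitoring Plan) has records looked at by an in-house quality program after the first patient's visit 1. A research nurse not directly involved in the study also audits them after the first 10 patients and at the halfway point of enrollment. Someone checking against the list could reasonably record each naive patient as a deviation.

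**Working it through.** **Step 1. Does the conflict touch the sample size?** The inputs from section VII (Sample Size and Power Calculation) are a rate of 0.85 in both arms, a margin of 0.15, one-sided alpha of 0.025 and power of 80%.

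n per arm = (z₀.₉₇₅ + z₀.₈₀)² × 2 × p(1 − p) / margin²

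= (1.960 + 0.842)² × 2 × 0.85 × 0.15 / 0.15²

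= 7.85 × 0.255 / 0.0225 ≈ 88.96, rounded up to 89 per arm and 178 in total.

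This reproduces the plan's figure. BTX history is not an input, so correcting the criterion changes nothing in this calculation.

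**Step 2. Apply the two sections to each type of patient**, all other criteria being met.

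| BTX history | Section IV (Methodology) | Section VI (both lists, as written) |
|---|---|---|
| None (naive) | May be offered enrollment; has its own stratum | Fails the inclusion item |
| Responder, last injection three months ago or more | Eligible | Eligible |
| Responder, only injection less than three months ago | Must wait for re-injection | Fails the inclusion item |
| Non-responder | Not eligible | Excluded |

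The sections agree in three of the four rows. They disagree in the first, and there completely.

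**Step 3. Look for a qualifier elsewhere.** None was found in the objectives, the schedule of research activities and its footnotes, the exclusion list or the analysis section. The schedule's three-month rule concerns repeat injections during the study.

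**Step 4. Consequence for the strata.** Under section VI as written, only the second row can enrol. The stratification factor then has one level, and stratifying by BTX history does nothing.

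**What cannot be computed.** The documents give neither the expected share of naive patients nor response rates by BTX history. The effect of a literal reading on accrual, or on the assumed rate of 0.85, therefore cannot be quantified.

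**The case against.** The strongest reply is that this is loose wording whose meaning any study team would recover. The Methodology names naive patients as a stratum, and its three-month interval applies only to re-injection. Other items in the lists also read as washout rules that apply where relevant. The two weeks off antimuscarinics or beta-3 agonists would, word for word, bar someone not taking them, and an instruction to switch off a neuromodulation device sits among the exclusions. This stands as an account of the cause: a drafting slip is much more likely than a deliberate restriction. It does not remove the conflict. The exclusion list writes explicit conditions for neuromodulation and for tibial nerve stimulation, so the authors did use such wording where they wanted it.

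Two stronger readings are tempting, and the documents do not support them.

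- *A reader might infer a loss of power.* If the criterion is applied literally, the trial still enrols 178 patients, all previously treated, and the planned power stands on the plan's own inputs. A loss would require naive patients to be enrolled and then removed, in a proportion that the documents do not give. Nor could the rate simply be held at 0.85 in a group selected for earlier response. If it were 0.90, for illustration, the plan's own table asks for only 63 per arm at 80% power.
- *A reader might infer that naive patients would drop out of the per-protocol analysis.* The plan says only "A completer analysis will be conducted for those who finish the study per protocol". It does not provide for removal on grounds of eligibility, and it also plans intent-to-treat analyses.

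**Conclusion.** The point holds as an internal inconsistency that is wrong as written. The inclusion item bars every BTX-naive patient, while the Methodology recruits and stratifies them. Applied literally, it leaves one stratum of two and a result confined to previous responders. Set aside in practice, it makes every naive enrolment a departure from a written criterion.

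The conclusion rests on the text alone and assumes only that inclusion criteria apply jointly. It does not dispute the sample size or the power, and it makes no claim about the composition of any analysis set. The intent can probably be recovered from the Methodology, so this is not fatal to the design. It should still be corrected, because it determines who may enter the trial.

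**What to change.** Reconcile the inclusion item with the Methodology by making it conditional, with the plan's own interval unchanged. For example: *If previously treated with onabotulinumtoxinA, the last injection was at least three months before enrollment; BTX-naive patients are eligible.* Referring to the last injection matches the Methodology's rule that all repeat injections be at least three months apart.

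This is a one-line protocol correction. It changes no sample size, visit, procedure or analysis.

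If the sponsor did mean to restrict the trial to previously treated patients, the item can stay, but the enrollment text and the stratification in the Methodology must then be rewritten. The aim and hypothesis should also say that they concern previous responders only. That would be a larger change, since it narrows the question the trial answers.

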#### Exclusion criteria:

- Pregnant or planning to become pregnant during study duration
- Diagnosis of neurogenic bladder with the exception of highly functioning stroke patients.
- If a patient has had a previous neuromodulation device placed, it will have to be turned off for 2 weeks for a washout period prior to enrollment and remain off throughout the study
- Previous non-responders to BTX therapy
- Known hypersensitivity to onabotulinumtoxinA
- Previous infection at onabotulinumtoxinA injection site
- Patient cannot be receiving PTNS therapy. If patient is receiving PTNS, they need to stop for 1 month prior to entering the study.
- Refusal to self-catheterize or have indwelling catheter in the event of urinary retention
- Use of investigational drug/device therapy within past 4 weeks
- Participation in any clinical investigation involving or impacting gynecologic, urinary or renal function within past 4 weeks
- Current or past history of any physical condition that, in the investigator's opinion, might put the subject at risk or interfere with study results interpretation

- Pelvic radiation treatment

#### VII. Data Analysis

**Statistical Analysis** 

#### Primary Effectiveness

The primary efficacy endpoint is defined as at least a 50% reduction in number of urgency related incontinence episodes at 3 months. The number of urgency incontinent episodes per day is measured as the average of two, 3-day, consecutive bladder diaries. Patients shall be classified as treatment successes or treatment failures based on this criterion.

The primary hypothesis is that the proportion of patients who are treatment successes with BTX-3 is non-inferior with a margin of 15% to that with BTX-10 at 3 months.

 $H_{o}: p_{BTX-3} \le p_{BTX-10} - 0.15 \text{ vs}$   $H_{a}: p_{BTX-3} > p_{BTX-10} - 0.15$ 

In the hypothesis equations, 0.15 is the clinical equivalence margin for the non-inferiority test of this hypothesis.

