The patient will receive BTX injections according to the group to which they have been randomized. If the patient has been randomized into the 3 injection group, they will receive an additional 7 "sham injections" with the needle retracted (no break in the mucosa). We decided on this as a sham treatment instead of actually puncturing the mucosa without injecting BTX because the point of our study is also to assess patient satisfaction and tolerability as well as rates of adverse events (ie hematuria and UTI). In order to do this, we want to puncture the mucosa less (3 vs 10). For the 3 injection group, every 3rd injection will be an actual mucosal penetration and injection (for 3 total injections containing BTX) in order to keep the patient blinded as best as possible. The 3 BTX injections will still be placed in the location as outlined in the diagram (Figure 1). The other 7 injection's will be verbally emphasized by the clinician but will not have mucosal penetration with the needle. It has been our experience that patients have variable sensation with needle penetration, sometimes no or minimal sensation to a clear sensation of a needle poke. The provider will verbalize the injection number to the patient whether it is a true injection or not in order to keep a believable pace. All patients will be told "This is injection #1. This is injection #2. This is injection #3." and so forth. Care will also be taken to prevent the patient from seeing the syringe so they cannot guess the arm of the study to which they were randomized. All patients will think they are receiving ten injections. Post-injection, the patient will be evaluated for hemostasis. Cautery will be used if deemed necessary by the physician. If hemostasis is achieved, this will conclude the visit.

If at the 2 week follow-up the patient has an elevated post-void residual (PVR) <350cc and is symptomatic or if the patient has a PVR > 350 cc and is non-symptomatic, the patient may be placed on either clean intermittent catheterization (CIC), one time straight catheter with close follow-up or indwelling foley catheter. Management for elevated post void residual

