#### V. Risks and Benefits

#### Possible Risks of OnabotulinumtoxinA:

Side effects and discomforts that have been observed in patients who have received treatment with this study medication for their OAB symptoms include:

Most Frequent (occurring more than 10% of the time):

 weakness of the bladder muscle resulting in difficulty in urination or an inability to urinate or empty the bladder (urinary retention) for an extended period (less than a month in most cases, but could be longer)

Less Frequent (occurring from 1% to 10% of the time):

- constipation
- Rare (occurring less than 1% of the time):
- generalized weakness

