#### Sample Size and Power Calculation

One hundred seventy-eight (178 patients will be randomized in this study, 89 per group to achieve 80% power to detect a non-inferiority margin difference between the group proportions of 0.15. The reference group (BTX-10) proportion is 0.85. The treatment group proportion (BTX-3) is assumed to be larger than 0.70 under the null hypothesis of inferiority. The power was computed for the case when the actual treatment group proportion is 0.85, that is both BTX-10 and BTX-3 had the same response rate of 0.85. The test statistic used is the one-sided Z test with a Type I error rate of 0.025.

Power	N1	N2	N	Reference (BTX-10) Responder Rate	BTX-3 Responder RatejH0	BTX-3 Responder Rate Ha
0.8	147	147	294	0.7	0.55	0.7
0.85	168	168	336	0.7	0.55	0.7
0.9	197	197	394	0.7	0.55	0.7
0.8	131	131	262	0.75	0.6	0.75
0.85	150	150	300	0.75	0.6	0.75
0.9	176	176	352	0.75	0.6	0.75
0.8	112	112	224	0.8	0.65	0.8
0.85	128	128	256	0.8	0.65	0.8
0.9	150	150	300	0.8	0.65	0.8

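### The month-3 responder rule says nothing about catheter use, so a patient with an indwelling catheter during the diary could count as a treatment success

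*Combined protocol and SAP*

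**What the plan says.** Section VII, Primary Effectiveness, sets the rule: "The primary efficacy endpoint is defined as at least a 50% reduction in number of urgency related incontinence episodes at 3 months". It adds: "Patients shall be classified as treatment successes or treatment failures based on this criterion". Neither sentence has a condition on catheter use or retention.

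Two further rules create failures. The text after the sample size tables counts patients who leave early because their symptoms did not improve enough. Injection Procedure (Section IV) and Data analyses (Section VII) count patients with no 3-month assessment. The four dropout scenarios in Data analyses also concern only dropouts.

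Elsewhere the plan expects catheters to be used:

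- Injection Procedure lists the options for a raised residual volume at the 2-week visit: intermittent catheterization, "one time straight catheter with close follow-up or indwelling foley catheter".
- Section V places bladder-muscle weakness in its most frequent class, above 10%, and describes the result as "urinary retention) for an extended period (less than a month in most cases, but could be longer".
- Section VI excludes anyone who would refuse a catheter if retention occurred.

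The Schedule of Research Activities has no item for catheter status. Residual volume is scheduled at the 2-week visits, after the first injection and after any re-injection, but not at month 3.

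**The concern.** An indwelling catheter drains the bladder continuously, so its user would be expected to record few or no urgency leaks whether or not the injection controlled the urgency. Under the stated rule that diary is a success. A complication of treatment would then be credited as efficacy, and without a catheter record the analyst could not reliably find these patients afterwards.

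This matters more in a non-inferiority comparison. If such patients were more common in the 3-site arm, the observed difference would move towards non-inferiority. Equal retention cannot simply be presumed: the same 100 U in 10 cc is given at about 33 U and 3.3 cc per site (100/3 and 10/3) in one arm and at 10 U and 1 cc per site in the other. Whether complications differ by arm is itself a secondary aim.

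**Working it through.** **Inputs from Section VII.** Margin 0.15. "The reference group (BTX-10) proportion is 0.85". "The test statistic used is the one-sided Z test with a Type I error rate of 0.025". The size is "89 per group to achieve 80% power to detect a non-inferiority margin difference between the group proportions of 0.15", with 0.85 assumed in both arms.

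**Plan's own figure.** n per arm = (1.960 + 0.842)² × [0.85×0.15 + 0.85×0.15] / 0.15² = 88.95, rounded up to 89. Power at 89 is 80.0%. The stated size reproduces.

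**Which rule reaches the patient.** Take a patient with an indwelling catheter who returns a month-3 diary. The patient has not left early and has been assessed, so neither extra failure rule applies. Only the diary criterion remains.

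**Effect on type I error.** Let c10 and c3 be the shares of each arm catheterised at month 3 and counted as successes. The documents give neither, so both are assumptions. Define truth as catheter = failure and put the true difference at the margin, holding the observed 10-site rate at 0.85. The true 10-site rate is 0.85 − c10 and the true 3-site rate is 0.70 − c10. The observed 3-site rate is then 0.70 − c10 + c3 = 0.70 + e, where e = c3 − c10. Only the excess e matters.

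P(declare non-inferiority) = Φ(e/SE − 1.960), with SE = √{[0.85×0.15 + (0.70 + e)(0.30 − e)]/89}.

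| Excess e in 3-site arm | SE | e/SE | Type I error |
|---|---|---|---|
| 0 | 0.0616 | 0 | 2.5% |
| +1 point (0.9 patients) | 0.0612 | 0.163 | 3.6% |
| +2 points (1.8 patients) | 0.0608 | 0.329 | 5.1% |
| +3 points (2.7 patients) | 0.0604 | 0.497 | 7.2% |
| −2 points (more in the 10-site arm) | 0.0623 | −0.321 | 1.1% |

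**A milder definition of truth.** Suppose only those who would have failed without the catheter are misclassified. At a 3-site success rate of 0.70, and with catheter use unrelated to response, that is 30% of them. An excess of 1 point becomes 0.3 points and gives 2.8%; 3 points becomes 0.9 and gives 3.5%.

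**Effect of reclassifying.** If an equal share of each arm moves from success to failure, the difference between arms is unchanged but the common rate p falls. Power = Φ(0.15/√[2p(1 − p)/89] − 1.960). At 1%, p = 0.84 and power is 77.9%. At 2%, p = 0.83 and power is 75.9%.

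**The case against.** The strongest reply is that few patients would be affected, for no known net effect. Section V says the weakness resolves within a month in most cases, and the endpoint is read at 3 months. Retention is tracked as an adverse event, and adverse events are compared between arms, so the harm is not hidden. Both arms receive 100 U, and the pilot study described in Section II reported similar adverse-event rates with one to three sites. Treating a catheter as failure is a choice of estimand, and part of the inflation shown above follows from that choice. All of this stands, and it keeps the point minor. It does not close the gap, because separate safety reporting does not change how the primary endpoint classifies the patient.

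Some stronger readings are tempting but unsupported:

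- *Every catheterised patient becomes a success because leakage stops.* The documents do not say this. Patients on intermittent catheterization can still leak and fail.
- *More than 10% in retention means about 9 patients per arm at 2 weeks.* The Section V item includes mere difficulty in urinating, is not a catheter rate and is not tied to that visit.
- *The 2-week results are distorted too.* Data analyses does say "This comparison will also be made for all other visits using t-tests or chi-square tests, as appropriate". But the catheter decision in Injection Procedure depends on the residual volume measured at the 2-week visit, where that diary is collected, so under that pathway the catheter follows the diary. The primary responder endpoint is defined only at 3 months.
- *The 3-site arm will have more retention.* The different amounts per site make this possible; nothing in the documents shows it.
- *One catheterised patient can decide the trial.* With 76/89 successes on 10 sites, the lower 95% limit is −4.5 − 1.96×5.60 = −15.5 points at 72/89 and −3.4 − 1.96×5.53 = −14.2 at 73/89. Any single patient at that boundary would do the same.

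**Conclusion.** The point holds in a limited form. The rule as written classifies a patient with an indwelling catheter at month 3 by the diary alone, and no other rule intervenes. That the diary would show few or no leaks is a reasoned inference. The number affected is unknown and probably small.

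Bias requires unequal catheter use at month 3, and it could run either way: about 3.6% to 7.2% type I error for an assumed excess of 1 to 3 points in the 3-site arm, less if some of these patients would have responded anyway, and below 2.5% if the excess lies in the 10-site arm. A reader might infer that the trial is biased towards non-inferiority or that the sample size is wrong. The documents support neither: the direction is unknown, and 89 per arm reproduces. The severity is minor.

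**What to change.** - In Section VII, Primary Effectiveness, state that a patient with an indwelling catheter during the month-3 diary is not counted as a treatment success.
- Keep the diary result for patients on intermittent catheterization in the primary analysis.
- Add a sensitivity analysis that counts all catheter users at month 3, of either kind, as failures in both arms.
- Record catheter type and start and stop dates on the visit form.

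The rule should not be extended to the 2-week diary, and catheter days should not be dropped from mean episode counts; if every diary day were affected, no value would remain. Settle the wording before the planned look at 3-month data once 25 patients per arm have been randomized.

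The cost is a sentence, a form field and one extra analysis, with a slightly lower observed success rate and the small loss of power shown above. How retention is managed does not change.
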